6 EFFICACY VARIABLES AND ANALYSES

Unless noted otherwise, the analyses of efficacy endpoints will be performed using the FAS. Efficacy data described below will be listed using the FAS.

6.1 Analysis of exploratory efficacy variables

The exploratory efficacy endpoints are measured on subject questionnaires and defined as:

- Change from baseline^a over time^b in sTST.
- Change from baseline^a over time^b in sLSO.
- Change from baseline^a over time^b in sWASO.
- Change from baseline^a over time^b in IDSIQ scores (i.e., total score; alert/cognition, mood and sleepiness domain scores).
- Change from baseline^a over time^b in the following visual analog scale (VAS) scores collected in the sleep diary: quality of the sleep, depth of the sleep, daytime alertness and daytime ability to function.
- Change from baseline (baseline as defined in Section 11.4) to Visit 3 (Week 14), Visit 4 (Week 27) and Visit 5 (Week 40) in ISI[®] scores.
 - The number and percentage of subjects with ≥ 6 points decrease in ISI[®] total score from baseline to Visit 3 (Week 14), Visit 4 (Week 27) and Visit 5 (Week 40) will be tabulated.
- Change from baseline^a over time^b in number of self-reported awakenings.
- Change from baseline (baseline as defined in Section 11.4) over time in PGA-S scores (daytime symptoms).
- Change from baseline (baseline as defined in Section 11.4) over time in PGI-C scores (daytime symptoms).

^a For subjects randomized to placebo in ID-078A301 or ID-078A302 and who are randomized to 25 mg ACT-541468 in this extension study, baseline is the mean value based on the last sleep diary / IDSIQ entries performed at home during a 7-day window (excluding any polysomnography [PSG] nights) in the confirmatory study. For all other subjects, baseline is the mean value based on the screening sleep diary / IDSIQ entries performed at home in the 7 days immediately preceding the first PSG at Visit 3 of the confirmatory studies.

^b Over time is the mean value of each time point defined in Table 6 (except for run-out week) based on the sleep diary / IDSIQ entries. According to the protocol it is planned to be completed at home daily during the last week of each consecutive 4-week double-blind study treatment period.

sTST (in minutes) is based on the time reported by the subject in item 9 of the sleep diary i.e., the answer to the question “In total, how long did you sleep last night?”.

sLSO (in minutes) is the self-reported time to fall asleep as reported in item 5 of the sleep diary, i.e., the answer to the question “How long did it take you to fall asleep?”.

sWASO is the self-reported time spent awake after sleep onset as reported in item 7 of the sleep diary, i.e., the answer to the question “In total, how long did these awakenings last?”.

The morning VAS consists of three questions: quality of subjects’ sleep, depth of sleep and sleepiness in the morning. The evening VAS consists of two questions: daytime alertness and ability to function. The VAS scores are collected in the sleep diary and answered on a continuous bipolar (or unipolar for sleepiness in the morning) scale ranging from 0–100 points; for all questions, a higher score reflects a better outcome.

The IDSIQ has 3 domains assessing Alert/Cognition, Mood, and Sleepiness [Table 2]. A total score can also be obtained. For each domain, the item responses in the respective domains are summed (each item is based on a categorical scale ranging from 0–10). Prior to summation, items 1, 2, 8, 10 and 14 must be reversed [see Table 2 for details regarding scoring]. For the Total score, all item responses are summed.

Table 2 Insomnia Daytime Symptoms and Impacts Questionnaire description

Domain	Scoring	Minimum/Maximum score
Alert/cognition	Daily: sum of Item 1*, Item 2*, Item 3, Item 9, Item 10*, Item 14*	Minimum score: 0 Maximum score: 60
	Weekly average: mean of the daily domain score over 7 days	Higher score: greater burden of illness
Mood	Daily: sum of Item 4, Item 5, Item 6, Item 7	Minimum score: 0 Maximum score: 40
	Weekly average: mean of the daily domain score over 7 days	Higher score: greater burden of illness
Sleepiness	Daily: sum of Item 8*, Item 11, Item 12, Item 13	Minimum score: 0 Maximum score: 40
	Weekly average: mean of the daily domain score over 7 days	Higher score: greater burden of illness
Total score	Daily: sum of all domains above	Minimum score: 0
	Weekly average: mean of the daily domain score over 7 days	Maximum score: 140 Higher score: greater burden of illness

* Item 1, Item 2, Item 8, Item 10, and Item 14 scores are reverse scored prior to summation.

A plot of the mean change from baseline over time (per month as defined in [Table 6](#)) for sTST, sWASO, sLSO and IDSIQ scores (i.e., Total score; Alert/Cognition, Mood and Sleepiness domain scores) will be provided together with a summary table.

Observed values and change from baseline over time in sTST, sWASO, sLSO and IDSIQ scores (i.e., total score; alert/cognition, mood and sleepiness domain scores) will be summarized by age group at screening in the confirmatory study (< 65; ≥ 65 years) and overall using descriptive statistics.

A longitudinal data analysis method (i.e., linear mixed-effects model) will be used for the analysis of change from baseline in sTST, sWASO, sLSO and IDSIQ scores (i.e., total score; alert/cognition, mood and sleepiness domain scores), separately. All available data, regardless of occurrence of intercurrent events (e.g., study treatment discontinuation, the use of prohibited medication), will be included in the model. Subjects who are randomized (switched) from placebo to 25 mg in this study will be excluded from this longitudinal analysis as their exposure to treatment and timing of assessments are not aligned with the other treatment groups.

The analysis model will adjust for the baseline value of the relevant response variable (either sWASO, sLSO, sTST or IDSIQ scores), age group as per assigned strata (< 65; ≥ 65 years), treatment (10 mg; 25 mg; 50 mg; placebo), visit (Month 6 [Week 12]; Month 9 [Week 24]; Month 12 [Week 36]; as defined in [Table 6](#)), and the interaction of treatment by visit, and baseline by visit (SAS[®] code available in [Appendix 1](#)).

An unstructured covariance matrix, shared across treatment groups, will be used to model the correlation among repeated measurements. A restricted maximum likelihood approach will be used to derive (unbiased) estimates of variance components. The Kenward-Roger approximation will be used to compute the denominator degrees of freedom and adjust standard errors [[Kenward 1997](#)]. If this analysis fails to converge, the use of the heterogeneous Toeplitz covariance structure, shared across treatment groups, will be explored.

Appropriate contrasts will be used to test the treatment differences of interest (i.e., the difference in least squares [LS] mean change from baseline between ACT-541468 10 mg vs placebo, ACT-541468 25 mg vs placebo and ACT-541468 50 mg vs placebo at Month 6, Month 9 and Month 12, see [Appendix 1](#)). Month 6 is the mean value based on the sleep diary / IDSIQ entries performed at home over the 7 days in Week 12 of the extension study; Month 9 (Week 24) and Month 12 (Week 36) are defined similarly.

The LS mean for each treatment group per time point will be displayed along with associated standard errors and 95% CIs. For each ACT-541468 dose level comparison with placebo, the placebo-adjusted LS mean will be displayed along with associated standard errors, 95% CI and unadjusted two-sided p-value.

Observed values and change from baseline over time in VAS scores, ISI[®], number of self-reported awakening, PGA-S and PGI-C will also be summarized using descriptive statistics.

Empirical cumulative distribution function plots of the observed cases of sWASO, sLSO, sTST and IDSIQ endpoints, separately, at Months 6, 9 and 12 for each treatment group will be provided. A summary will be provided showing the cumulative number and percentage of subjects meeting certain thresholds for sWASO, sLSO, sTST and IDSIQ endpoints, separately, for the observed range of values.

For sTST, sWASO, sLSO, each IDSIQ domain and total scores, VAS scores and number of self-reported awakenings, subjects must have at least 2 days of data during each week to calculate a weekly mean. Otherwise, the mean value will be considered missing for that week. The approaches above imply implicit imputation: the missing data points are given the same value as the mean of the non-missing data points of that same time point or week.

Subgroup analyses for sTST, sWASO, sLSO, each IDSIQ domain and total scores endpoints will be performed to investigate the consistency of the treatment effect (i.e., ACT-541468 vs placebo) across subgroups defined as:

- Age at screening of confirmatory study: $< 65, \geq 65$ years and $< 75, \geq 75$ years.

Specific subgroup analyses for sTST and each IDSIQ domain and total scores endpoints are defined below:

- Sex: Male, female.
- Region: US, other (non-US).
- BMI at screening of confirmatory study: $< 30, \geq 30$ kg/m².
- Race: White, Black or African American, Other*;

* The 'Other' category will not be considered for subgroup analyses due to the mix of races and small number of subjects limiting the ability (i.e., low power) to detect differences between treatment groups. 'Other' includes: American Indian or Alaska Native, Native Hawaiian or other Pacific Islander, Asian and Other (Entry for multiple races was to be reported under category 'Other'. Similarly, 'Not permitted as per legislation/regulation' was to be also grouped within this category 'Other').

The same model as for the longitudinal analysis (i.e., linear mixed-effects model) will be fitted with the additional factor for subgroup, and the interaction of subgroup by treatment, subgroup by visit, and subgroup by treatment by visit. Subjects who are randomized (switched) from placebo to 25 mg in this study will be excluded from these longitudinal analyses.

Of note, age group will not be included as a covariate in the model of the subgroup analyses by age.

Treatment effect estimates (LS mean and associated 95% CI for the ACT-541468 comparison with placebo) at Month 6, 9 and 12 will be presented via forest plots.

At the time of interim analysis, treatment will still be ongoing for some subjects so the efficacy beyond 6 months should be interpreted with caution.

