11.4 Baseline

Unless otherwise defined in the specific analysis section, baseline is defined as follows:

1. For subjects entering ID-078A303 and assigned to the same treatment arm as that of the confirmatory studies (ACT-541468 10 mg, 25 mg, or 50 mg, or placebo), baseline is the last non-missing assessment performed or value measured before or on the day of first dose of double-blind study treatment in the confirmatory study.
2. For subjects entering ID-078A303 who received placebo in the confirmatory studies and who are randomized (switched) to 25 mg of ACT-541468 in the extension study, baseline is the last non-missing assessment performed or value measured before or on the day of first dose of double-blind study treatment in the extension study. This could be either data collected at Visit 1 of the extension study or collected in the confirmatory study. An assessment taken on the day of the double-blind study treatment start date is considered a baseline assessment and is not considered a post-baseline assessment in the double-blind study period.

Subjects with no data on a particular parameter before the first treatment administration will have a missing baseline (and change from baseline) for this parameter.

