Table 7 Time windows (in days) for PGA-S and PGI-C measurements

Week	Reference 7-day window (Study day)	Time window (Study day)
4	22–28	(20; 35)
8	50–56	(48; 63)
12*	78–84	(76; 91)
16	106–112	(104; 119)
20	134–140	(132; 147)
24*	162–168	(160; 175)
28	190–196	(188; 203)
32	218–224	(216; 231)
36*	246–252	(244; 259)
40	274–280	(272;287)

* Week 12, 24 and 36 correspond to Month 6, 9 and 12, respectively.

Values from the run-out period will not be included.

PGA-S = Patient Global Assessment of Disease Severity; PGI-C = Patient Global Impression of Change.

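### SAP Section 6.1 defines the PGI-C endpoint as a change from baseline, but PGI-C is by name already a rating of change, so the result is either missing or a difference of two change ratings

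*SAP*

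**What the plan says.** Section 6.1 of the SAP lists the exploratory efficacy endpoints. The last two bullets treat PGA-S and PGI-C in identical terms. The PGI-C bullet reads "Change from baseline (baseline as defined in Section 11.4) over time in PGI-C scores (daytime symptoms". The note to Table 7 in Section 11.7 expands the name: "PGI-C = Patient Global Impression of Change".

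Later in Section 6.1, one sentence plans both observed values and change from baseline for a list of measures. It ends "number of self-reported awakening, PGA-S and PGI-C will also be summarized using descriptive statistics".

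Section 11.4 sets two baselines. For subjects "assigned to the same treatment arm as that of the confirmatory studies (ACT-541468 10 mg, 25 mg, or 50 mg, or placebo" it is the "last non-missing assessment performed or value measured before or on the day of first dose of double-blind study treatment in the confirmatory study". For subjects switched from placebo to 25 mg it is the "last non-missing assessment performed or value measured before or on the day of first dose of double-blind study treatment in the extension study", and the SAP adds: "This could be either data collected at Visit 1 of the extension study or collected in the confirmatory study". Where nothing was recorded in time, "Subjects with no data on a particular parameter before the first treatment administration will have a missing baseline", and the change from baseline is missing too.

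Section 11.5 defines change as the later value minus the baseline value, for every variable.

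**The concern.** Subtracting a baseline suits a severity scale such as PGA-S: severity before treatment is a meaningful quantity, and the difference measures improvement. A rating of change already contains the comparison with an earlier state. Subtracting a second value requires a change rating from before treatment, which may not exist and has little meaning if it does.

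At stake is one endpoint and one table. The table could come out empty in some columns, or it could hold numbers that look like improvement scores and are not. Section 10 says that every analysis in the SAP is also run at the interim analysis that supports regulatory filings, so the same table would appear there as well.

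**Working it through.** No sample size, power or error rate is involved and there is no figure of the plan to reproduce. The check applies the SAP's own rules to PGI-C, arm by arm.

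**Inputs**

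1. Endpoint: change from the Section 11.4 baseline (Section 6.1, endpoint list, and again in the descriptive-summary sentence).
2. Nature of the measure: a rating of change (abbreviation list; Table 7 note).
3. Formula (Section 11.5): change = post-baseline PGI-C − baseline PGI-C.
4. Baseline (Section 11.4): on or before the first confirmatory dose for the four continuing arms (10 mg, 25 mg, 50 mg, placebo); on or before the first extension dose for ex-placebo/25 mg.
5. Missing-baseline rule (Section 11.4): no value in time means no baseline and no change.
6. Post-baseline values: the ten Table 7 windows, Week 4 to Week 40. The earliest opens at Study Day 20, so none of them can supply a baseline.

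**Is there an exception elsewhere?** Section 11.4 gives way to a baseline defined in a specific analysis section. Section 6.1 has its own baseline in footnote a, but that footnote covers sleep diary and IDSIQ entries. The PGI-C bullet does not carry it and points to Section 11.4 instead. Section 12.3, on clarifications of endpoint definitions, deals only with adverse event tables. So the general rule applies.

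**What is unknown.** The documents do not say when PGI-C was collected in the confirmatory studies, or whether it is collected at extension Visit 1. They also do not give the item's wording, its reference point or its response scale. Each possibility is therefore worked through.

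| Group | PGI-C available on or before the relevant first dose? | Result under Sections 11.4 and 11.5 |
|---|---|---|
| Four continuing arms | No | Baseline missing, change missing |
| Four continuing arms | Yes, taken before or on the day of the first confirmatory dose | Extension change rating minus a change rating from before double-blind treatment |
| Ex-placebo/25 mg | No | Baseline missing, change missing |
| Ex-placebo/25 mg | Yes, from the confirmatory study or extension Visit 1 | Extension change rating minus an earlier change rating, possibly one given after the placebo period |

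**Reading the table.** In rows 1 and 3 nothing can be computed. In rows 2 and 4 a number exists, but it is a change of a change. In row 4, for example, a subject who gave rating r after placebo and the same rating r on 25 mg scores r − r = 0, whatever r was. The zero does not distinguish a subject who felt better both times from one who felt worse both times.

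Rows 2 and 4 also subtract ratings from different stages: before any double-blind treatment in the continuing arms, possibly after months on placebo in the switched group. Even where both columns are filled, they do not measure the same thing.

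No branch yields a usable measure of improvement, so the conclusion does not depend on the unknown schedule.

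**The case against.** The best defence is that little is lost. The sentence in Section 6.1 that plans the change also plans observed PGI-C values. Table 7 supplies the reporting windows, and Section 9.1 gives treatment-group columns and counts with percentages for categorical variables. No PGI-C test is planned: the mixed model covers only sTST, sWASO, sLSO and IDSIQ. Efficacy is exploratory and the primary objective is safety. All of this stands, and it limits the impact. It does not repair the definition, because the endpoint list names only the change, and the summary sentence commits to tabulating it.

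A reader might go further and infer three things that the documents do not support.

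- **That the endpoint is missing for everyone in the four continuing arms.** The Section 11.4 rule is conditional on there being no value in time. Missingness is likely, since a rating of change has little meaning before treatment. But Section 7.8 shows that the confirmatory study had a run-in with assessments at Visit 3, and nothing says whether PGI-C was among them.
- **That the ex-placebo/25 mg group certainly gets a change of a change.** This requires that a PGI-C was collected by the first extension dose, which is not stated. If none was, the result is missing there too.
- **That PGI-C allows no comparison between arms.** This is true only of the change-from-baseline summary. Observed ratings by arm can still be compared descriptively.

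**Conclusion.** The definition is wrong as written, with minor impact. By the SAP's own rules, a change from baseline in PGI-C is either missing or a difference between two change ratings, and the rating subtracted comes from a different stage in the continuing arms than in the ex-placebo/25 mg group.

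The conclusion rests on one premise, that the instrument is what its name says. It needs no assumption about the collection schedule. The schedule decides only which form the fault takes in each arm, so no percentage of missing values can be given.

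The fault lies in one endpoint definition and one descriptive summary. No test, model or primary result is affected.

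**What to change.** - In the Section 6.1 endpoint list, replace the PGI-C change from baseline by the observed PGI-C rating at each Table 7 window, by treatment group.
- In the later Section 6.1 sentence on descriptive summaries, restrict PGI-C to observed values. Both places need the edit; correcting only the endpoint list would leave the summary in the plan.
- Say how the rating is presented, for example number and percentage by category.
- State for each arm the point in time to which the rating refers, so that the continuing arms and the ex-placebo/25 mg group can be read correctly side by side.
- Leave PGA-S as it is: change from baseline is sensible for a severity scale.

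The cost is two text edits, one sentence on the reference point and one table shell. No data collection, model or other analysis changes. If the main protocol uses the same wording for PGI-C, the departure should also be recorded in SAP Section 12.

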**For subjects potentially transitioning from ID-078A302 to ID-078A303 [protocol section 7.1.1]:**

- New enrollment in the extension study is allowed only if Visit 1 in ID-078A303, as well as Visit 10 in ID-078A302 can happen on-site.

**2.2 Conduct of remote visits for subjects who cannot, are not allowed to, or are not willing to travel to the investigator's site**

- If the subject cannot, is not allowed to, or is not willing to travel to the investigator's site, the clinic visit(s) can be replaced by a **telephone call or video call**: to keep close contact with subjects (remote visits), these visits should be at least as frequent as the protocol-mandated clinic visits.
  - The investigator should notify the IEC / IRB in advance of remote visits if this is a local requirement.

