2 STUDY DESIGN AND FLOW

Subjects who complete double-blind study treatment and the run-out period of the confirmatory study, and who are willing to participate, will be eligible to enter the ID-078A303 extension study.

The ID-078A303 study will be offered at every site participating in ID-078A301 and ID-078A302 (approximately 150 centers in 17 countries), and to every eligible subject.

[figure not shown]
Subjects assigned to the placebo arm in the confirmatory study will be randomized to receive either placebo or 25 mg ACT-541468 in a 1:1 ratio in the extension study. Treatment allocation will be stratified by age into 2 categories: < 65 and ≥ 65 years (the age entered at the screening visit of the confirmatory study will be taken into consideration for the randomization in the extension study).

Subjects assigned to one of the ACT-541468 arms in the confirmatory study will continue on the same dose (but assigned a new randomization number).

It was expected that approximately 1260 subjects (i.e., ~70% of the total subjects in the combined confirmatory studies) would enter the extension study after completing the

confirmatory study. The overall study design, including the transition from the confirmatory study, is depicted in [Figure 1](#).

Figure 1 Study design

.....> Monthly telephone call.

EODBT = end-of-double-blind treatment; EOS = End-of-Study; EOT = End-of-Treatment.

Subjects randomly assigned to the ACT-541468 arms in the confirmatory studies will receive the same dose in the extension study.

Subjects randomly assigned to the placebo arm in the confirmatory studies will be randomized to receive either placebo or 25 mg ACT-541468 in a 1:1 ratio in the extension study.

The study comprises 2 phases:

- The **double-blind treatment phase** starts when the treatment is allocated (Visit 1) and lasts 40 weeks, until the EODBT at Visit 5.
- The **safety follow-up phase** starts from the EODBT and ends 30 days after the last dose of double-blind study treatment with the EOS at Visit 7. It consists of the following two periods:
 - A single-blind placebo run-out period of 7 days (from the evening of Visit 5 until after all visit assessments have been performed at Visit 6 i.e., EOT).
 - A safety follow-up period (from EOT until EOS).

See Section 11.2 for a detailed definition of study periods.

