5.1.4 Study enrollment

The number and percentage of subjects enrolled as well as subjects enrolled but not randomized will be displayed by country and site based on the ENR Set.

The number and percentage of subjects randomized will be displayed by country and site based on the FAS by treatment group and all treatment groups combined.

The randomization scheme and codes will be listed for randomized subjects only using the FAS.

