10 INTERIM ANALYSES

This study includes an IDMC and ISB that will assess safety of ACT-541468 on a regular basis as per IDMC and ISB charters, respectively.

Safety and efficacy data supporting the review by IDMC will be provided by Idorsia for the part of analyses that are blinded and by an ISAC for the unblinded part.

An interim analysis was introduced as part of amendment protocol Version 3, dated 17 February 2020, to support global regulatory filings.

The interim analysis will be conducted when all subjects who did not prematurely discontinue study treatment have reached Visit 3.

A second interim analysis may be performed to fulfil the FDA requirement to submit updated safety data 120 days after NDA submission from ongoing studies, in case the study has not been completed by that time.

To maintain the integrity of the study after the interim analysis, participating subjects as well as investigators will remain blinded for the entire duration of the study. The sponsor personnel involved in data collection and medical monitoring of the study will also remain blinded until the end of the study.

The interim analysis will be based upon a snapshot of the clinical trial database and will include all clean safety and efficacy data as of approximately end of July (a cut-off date

will be fixed to ensure all subject data up to and including Visit 3 are included). All visits and assessments that have been done before and on this cut-off date will be considered for the interim analysis. All analyses described in this SAP will be performed for the interim analysis.

SDTM dataset will be based on the snapshot of the clinical database and may include data beyond the cut-off date. Then, ADaM datasets will be produced including only data up to the date of the interim cut-off.

No adjustment for multiple testing is required as no formal interim analysis will be performed for determining whether to stop (or modify) the study (i.e., no hypothesis testing will be conducted ad interim).

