14 APPENDICES

Appendix 1 SAS[®] code for Mixed Model for Repeated Measures

```
ods output sliceDiffs=lsd2;  
proc mixed data=data;  
  class SUBJID AGE TRT VIS;  
  model CHG = BASE AGE TRT VIS TRT*VIS BASE*VIS/ ddfm= kr;  
  repeated VIS / subject=SUBJID type=un;  
  lsmeans TRT*VIS / cl alpha=0.05;  
  slice TRT*VIS / sliceby=VIS diff=control('PLACEBO' 'Month12') cl;  
run;  
ods output close;
```

/* The following code could be used as reference */

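### The pooled efficacy model has no parent-study term although the active doses are inherited from two separately randomised studies

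*SAP*

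**What the plan says.** SAP 1 describes one joint extension of ID-078A301 and ID-078A302. On allocation, SAP 2 states: "Subjects assigned to one of the ACT-541468 arms in the confirmatory study will continue on the same dose". Only subjects who had placebo in a parent study are randomised in the extension, 1:1 to placebo or 25 mg. For that step, "Treatment allocation will be stratified by age into 2 categories"; parent study is not a stratum.

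For efficacy, SAP 6.1 states: "The analysis model will adjust for the baseline value of the relevant response variable". It adds age group, treatment at four pooled levels, visit (Months 6, 9 and 12), treatment-by-visit and baseline-by-visit. Appendix 1 agrees: "model CHG = BASE AGE TRT VIS TRT*VIS BASE*VIS/ ddfm= kr". Subjects switched from placebo to 25 mg are excluded. The subgroup models are built on the same base model. Each dose is compared with placebo at each of the three months, with a 95% CI and an unadjusted two-sided p-value.

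Parent study does not appear among the 6.1 subgroup factors (age, sex, region, BMI, race). Nor does it appear in the enrolment tables of 5.1.4: "The number and percentage of subjects randomized will be displayed by country and site based on the FAS".

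**The concern.** With the switched subjects removed, no modelled contrast compares arms that were randomised against each other in the extension. The 10, 25 and 50 mg arms were formed by randomisation within ID-078A301 or ID-078A302. The placebo arm is a random half of those studies' placebo subjects who rolled over. The protected comparison is therefore within parent study, yet the model pools the studies as though they were one. It adjusts for the extension's age stratum but not for the study in which the compared arms were allocated.

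Bias needs two things together: a different study mix in a dose arm and in placebo, and a study difference in mean change that baseline and age do not absorb. If both hold, the contrast is shifted and its CI and p-value are wrong. Two doses drawn mainly from different studies would be shifted in opposite directions, which would distort the apparent dose-response. The planned tables would not show it, because none crosses arm with parent study.

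The interim adds a second route to an uneven mix. The COVID-19 addendum (2.1) describes entry as still open from ID-078A302 only: "New enrollment in the extension study is allowed only if Visit 1 in ID-078A303, as well as Visit 10 in ID-078A302 can happen on-site". The interim (SAP 10) "will include all clean safety and efficacy data as of approximately end of July". Whether a subject has Month 9 and Month 12 values by then may depend partly on parent study.

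**Working it through.** **Inputs from the documents.** About 1260 entrants, stated as about 70% of the parent total (SAP 2), which implies 1260/0.70 = 1800. Ex-placebo subjects are split 1:1. There are three modelled visits. The plan gives no efficacy SD, effect size or power, so there is no stated figure to reproduce.

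**Assumptions.** The doses in each parent study and the numbers per arm and study are not in the text. Two layouts of 1260 bracket the possibilities, with equal parent arms in each:

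- Layout A: every dose in both studies, same mix in all arms; 315 per dose, 157.5 on placebo.
- Layout B: one dose in one study only, another dose in the other study only, one dose shared; 210 per dose per study, placebo 105 + 105.

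The residual study difference d is taken as 0.1 to 0.2 SD.

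**Bias without a study term.** Bias = d × (share of the arm from one study − share of placebo from that study). In Layout B a one-study dose has share 1 against 0.5, a difference of 0.5.

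**Standard error.** For any dose in A: √(1/315 + 1/157.5) = 0.0976 SD. For a one-study dose in B: √(1/210 + 1/210) = 0.0976 SD.

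**Rejection rate** of a two-sided 5% test when the true effect is zero, Φ(−1.96 + bias/SE) + Φ(−1.96 − bias/SE), with SE 0.0976:

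| Share difference | Bias, d = 0.1 to 0.2 | Rejection rate |
|---|---|---|
| 0 | 0 | 5.0% |
| 0.25 | 0.025 to 0.05 SD | 5.8% to 8.1% |
| 0.5 | 0.05 to 0.10 SD | 8.1% to 17.6% |

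A simulation of Layout B (1000 runs, one visit, no true effect) agrees. At d = 0.1 the bias was about ±0.05 SD with rejection about 8%; at d = 0.2 it was about ±0.10 SD with about 17%. The two one-study doses had opposite signs and the shared dose was unbiased.

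**With a study term.** In Layout B the study difference is estimated within the shared dose (210 v 210, information 105) and placebo (105 v 105, information 52.5), total 157.5. The bias falls from 0.50d to 0. The SE of a one-study dose becomes √(2/210 + 0.5²/157.5) = 0.1054 SD, a rise of 8.0%. An effect with 80% power at SE 0.0976 is (1.960 + 0.842) × 0.0976 = 0.273 SD; at SE 0.1054 its power is 74%. In Layout A the bias is 0 and the SE unchanged, with or without the term.

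**Interim.** Assume a cut-off of 31 July 2020. A subject entering on 31 March 2020 is then at Study Day 123, before the Month 9 window opens at Day 157 (Table 6). Two diary days in the Month 9 window (Days 157–158) need entry by 25 February 2020; in the Month 12 window (Days 241–242), by 3 December 2019. Generalised least squares was run on three visits with compound-symmetric correlation 0.4 to 0.8. Assumed availability at Month 9 / Month 12 was 90–100% / 60–100% in one study and 40–60% / 10–30% in the other. In Layout B the unadjusted Month 12 contrast carries about 0.3 to 0.7 of d, and the adjusted contrast carries none. The SE rise is from about 2% to a little over 20%. In Layout A the bias is 0 at the interim too, so uneven availability alone creates no bias.

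**The case against.** The strongest objection is that the deciding fact is out of view. The only protocol document available is the COVID-19 addendum, and Figure 1 of the SAP is not shown. The doses per parent study may well be stated elsewhere, and the arms may share the same mix, in which case nothing is wrong. This stands: the point is a risk to check, and imbalance has not been shown.

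Both factors of the bias are also assumed. The studies feed one extension with the same diary and windows, and all modelled subjects have the same pre-treatment baseline definition, so d may be small. The 17.6% needs d = 0.2, a share difference of 0.5 and complete data. If 70% of subjects contribute, the SE is 0.0976/√0.70 = 0.117 and the rate is 13.7%. This limits the size but leaves the structure as it is.

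Where the mixes differ, the term costs precision. In Layout B the unadjusted model has the lower mean squared error unless d exceeds √(0.1054² − 0.0976²)/0.5 ≈ 0.08 SD. That is fair for a point estimate. The plan also reports CIs and p-values, however, and their validity depends on bias.

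Finally, efficacy is exploratory, 6.1 already urges caution beyond 6 months at the interim, and no stopping decision depends on the result. This keeps the priority low. The term also does nothing about selection of completers who choose to roll over.

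**Conclusion.** The concern holds as a conditional weakness of low priority. The text and the code both omit parent study, while the modelled contrasts depend on randomisation within parent study. Under the stated layouts and d = 0.1 to 0.2 SD, the effect ranges from none (equal mixes) to a bias of 0.05 to 0.10 SD with 8.1% to 17.6% rejection (share difference 0.5). A larger study difference would give more. Whether any bias exists depends on arm-by-study counts and a between-study difference that the documents do not give. The primary safety objective is not affected.

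**What to change.** Add parent study and its interaction with visit to the SAP 6.1 model, to the subgroup models and to Appendix 1:

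`class SUBJID AGE STUDY TRT VIS;`
`model CHG = BASE AGE STUDY TRT VIS TRT*VIS BASE*VIS STUDY*VIS / ddfm=kr;`

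Add arm-by-parent-study counts to 5.1.4. For the interim, also give the number of subjects with Month 6, 9 and 12 values by arm and parent study. State in 6.1 that the term removes an additive study difference only: it does not correct a shift in weighting if the treatment effect itself differs between studies.

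The cost is three fixed-effect parameters (one for study, two for study-by-visit), one SAP sentence and one table. Parent study is known for every subject. If arms are balanced over studies, there is no loss of precision. If a dose comes from one study only, its SE rises by about 8% at the final analysis, and by more in some interim Month 12 scenarios, under the assumptions above.
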